Specific Aim 1. To determine the safety and efficacy of ixazomib as a desensitization strategy. There is currently no effective desensitization strategy for highly sensitized patients defined as calculated Panel of Reactive Antibodies (cPRA) $\geq 80\%$. For this study, 10 highly sensitized kidney transplant candidates on the waitlist for more than 24 months will receive ixazomib 3 mg (and dexamethasone 20 mg) on days 1, 8, and 15 of a 28 cycle for 12 months. The primary objective is to evaluate the safety (distal neuropathy, thrombocytopenia, and gastrointestinal symptoms) and efficacy (decline in cPRA $> 20\%$) of ixazomib. The secondary efficacy endpoint is transplantation rate within 12 months of therapy.

Specific Aim 2. Identify immune indices which predict the course of disease and/or response to treatment in highly sensitized patients. Mechanistic studies will use bone marrow and blood obtained from subjects in Aim 1 to determine the effect of treatment on immune regulation and reconstitution after therapy. Since the bone marrow microenvironment produces BAFF/APRIL and supports plasma cell maturation, we will determine the effect of therapy on the generation of BAFF/APRIL by bone marrow mesenchymal stem cells and the survival of bone marrow-derived plasma cells after desensitization. We specifically propose to:

- Identify if bone marrow plasma cells, IgG subsets, and levels including free light chains, and circulating BAFF/APRIL predict outcomes.
- Determine if treatment is effective in downregulating circulating BAFF/APRIL and anti-HLA, endothelin-1 type A receptor (ETAR), angiotensin type 1 receptor (AT1R), and complement fixing C1q antibodies.

Figure 1. Protocol Summary

| |
|--|
| Study Title: IXAzomib for DESensitization (IXADES) |
| Phase: II |
| Number of Patients: 10 |
| Study Objectives The primary objective is to evaluate the efficacy of ixazomib in desensitizing highly sensitized kidney transplant recipient, defined as a decline in calculated PRA (cPRA) > 20%, or successful transplantation within 12 months. The secondary objective is to determine the toxicity and tolerability of ixazomib with particular focus on distal neuropathy, thrombocytopenia, and gastrointestinal symptoms. |

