2. STUDY OBJECTIVES

2.1 Primary Objectives

Specific Aim 1. To determine the safety and efficacy of ixazomib as a desensitization strategy. 10 highly sensitized kidney transplant candidates on the waitlist for more than 24 months will receive ixazomib 3 mg (and dexamethasone 20 mg) on days 1, 8, and 15 of a 28 cycle for 12 months. The primary objective is to evaluate the safety (distal neuropathy, thrombocytopenia, and gastrointestinal symptoms) and efficacy (decline in cPRA > 20%) of ixazomib. The secondary efficacy endpoint is transplantation rate within 12 months of therapy.

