3. STUDY ENDPOINTS

3.1 Primary Endpoints (safety and efficacy)

Primary efficacy and safety endpoint:

- Efficacy endpoint: A decline in cPRA > 20%.
- Safety endpoint: infections, malignancies, hematological complications including leucopenia, anemia, and thrombocytopenia, cardiovascular complications and events, distal neuropathy, gastrointestinal symptoms, and immunosuppression-related adverse effects.

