7. STATISTICAL AND QUANTITATIVE ANALYSES

7.1 Statistical Methods

More than 50% of patients with CDC T cell crossmatch titers $\geq 1:8$ and/or cPRA $> 80\%$ fail to respond to desensitization (5, 8). In this pilot exploratory, proof of concept, open-label, single-center phase II clinical trial, we hypothesize that our study will have a higher rate of transplantation. [name], PhD, epidemiologist and biostatistician in the division of nephrology, will perform the statistical analyses. *Primary* efficacy (decline in cPRA $> 20\%$) and safety (discontinuation of therapy due to adverse events) endpoint will be analyzed using the exact binomial test. The *secondary* endpoint (time to transplantation) will be assessed using Kaplan-Meier analyses and log rank tests. Baseline characteristics will be compared between participants with and without the primary end point using the 2-sample t test for continuous variables and the Fisher's exact test for categorical variables. Relationships between serum BAFF/APRIL, antibodies, and baseline cPRA will be assessed using the Pearson correlation coefficient. The influence of serum BAFF/APRIL, antibodies, and bone marrow plasma cells on end points of interest will be investigated using Kaplan-Meier curves and Cox proportional-hazards models.

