7.1.1 Determination of Sample Size

The primary outcome will be considered as a dichotomous outcome (decline in cPRA of $>20\%$ or not). We will test the hypothesis that the success rate (i.e., the % that have a decline in cPRA $>20\%$) is 0% using the exact binomial test (Figure 2a) (5). The figure shows the lower and upper 95% confidence limits resulting from any observed success rate. For example, if we observe success in 3/10 (30%), the resulting 95% confidence interval (CI) is (6.7%, 65.2%). Any observed success demonstrates that the success rate of the proposed treatment is >0 . Figure 2b represents the power curve, that is, the probability of observing any success, given different values of true success rate. For example, we would have $> 80\%$ chance of observing at least one success if the true success rate is > 0.2 .

Figure 2a. Sample Size Analysis

[figure not shown]
[figure not shown]

Figure 2b. Power curve

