7.1.3 Populations for Analysis

All patients enrolled will be included in the safety analysis.

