8.1 Definitions

8.1.1 Adverse Event Definition

Adverse event (AE) means any untoward medical occurrence in a patient or subject administered a pharmaceutical product; the untoward medical occurrence does not necessarily have a causal relationship with this treatment. An AE can therefore be any unfavorable and unintended sign (including an abnormal laboratory finding), symptom, or disease temporally associated with the use of a medicinal (investigational) product whether or not it is related to the medicinal product. This includes any newly occurring event, or a previous condition that has increased in severity or frequency since the administration of study drug. AEs will be assessed at study visits and during the final follow-up study visit. In addition, data on rejection, graft, and patient survival will be collected for 6 months following kidney transplantation.

An abnormal laboratory value will not be assessed as an AE unless that value leads to discontinuation or delay in treatment, dose modification, therapeutic intervention, or is considered by the investigator to be a clinically significant change from baseline. These AEs will be entered into the OnCore system.

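### Section 7.1 tests a primary safety endpoint that 3.1 does not define, without a null rate, and 9.1 withholds a judgement that 8.1.1 needs to count some laboratory changes as adverse events

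*Combined protocol and SAP*

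**What the plan says.** **The safety endpoint.**
- Protocol Summary, objectives row: "The secondary objective is to determine the toxicity and tolerability of ixazomib with particular focus on distal neuropathy, thrombocytopenia, and gastrointestinal symptoms". Specific Aim 1 in the same summary places safety in the primary objective.
- Section 2.1: "The primary objective is to evaluate the safety (distal neuropathy, thrombocytopenia, and gastrointestinal symptoms) and efficacy".
- Section 3.1: "Safety endpoint: infections, malignancies, hematological complications including leucopenia, anemia, and thrombocytopenia, cardiovascular complications and events, distal neuropathy, gastrointestinal symptoms", followed by adverse effects of immunosuppression. The summary's endpoints row repeats this list. Section 7.1.8 says the safety analysis will focus on it, and 9.1 gives it to the DMC as the safety data to review.
- Section 7.1: the primary "safety (discontinuation of therapy due to adverse events) endpoint will be analyzed using the exact binomial test".
- Section 7.1.1 gives the plan's only null. It is for cPRA response, whose success rate under the null "is 0% using the exact binomial test".
- Section 7.1.3: "All patients enrolled will be included in the safety analysis". Section 4.2 sets enrolment at 10.

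**Laboratory changes.** Section 8.1.1 says: "An abnormal laboratory value will not be assessed as an AE unless that value leads to discontinuation or delay in treatment, dose modification". It adds therapeutic intervention as a further route, and finally the case where the value "is considered by the investigator to be a clinically significant change from baseline". Section 9.1 says that laboratory results abstracted from the medical record are expected to be abnormal in this population, and that the PI will not classify them as clinically significant or not.

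**The concern.** Two parts of the plan give the label of primary safety endpoint to different things, and the version that is tested has no reference rate. The same 10 patients could yield different primary safety results, and the choice could be made after the data are seen. Safety is half of the primary aim in this single-arm, open-label trial, and the DMC is to receive an analysis of the primary outcomes (9.1), so it matters which outcome that is.

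The laboratory rules raise a separate problem. One route by which a laboratory change becomes an adverse event depends on a judgement that another section says the PI will not make. If no one else makes it, a low count of laboratory adverse events could not be read as an absence of laboratory change.

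**Working it through.** **1. The plan's own figures.** Section 7.1.1 gives an exact 95% CI of 6.7% to 65.2% for 3/10. The Clopper-Pearson interval is 6.67% to 65.25%, which agrees. It also gives a chance above 80% of at least one success when the true rate exceeds 0.2: 1 − 0.8^10 = 0.893, which agrees. Both figures concern efficacy. The plan gives no figure for safety.

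**2. How many contents.** Side by side, the statements of safety have three contents:
- three toxicities (summary objectives row, 2.1);
- a broad list of event classes with no summary measure (summary endpoints row, 3.1, 7.1.8, the DMC text in 9.1);
- stopping therapy because of an adverse event (7.1 only).

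The objectives row differs from 2.1 in rank, secondary against primary, rather than in content.

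**3. The missing null.** For x discontinuations in n = 10, the one-sided exact p is P(X ≥ x | 10, p0). The plan gives no p0, so the values below are assumptions. For x = 3:

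| Assumed p0 | p |
|---|---|
| 5% | 0.012 |
| 10% | 0.070 |
| 20% | 0.322 |

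If the efficacy null of 0% were borrowed, P(X ≥ 1 | p0 = 0) = 0, so a single discontinuation would reject. That says nothing useful about tolerability.

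**4. What changes with the definition.** If 3.1 is read as a patient having any listed event, the rate cannot be lower than the rate for gastrointestinal events alone. Tables 3-2 and 3-3 give 160/201 = 79.6% and 139/173 = 80.3%, or about 8 of 10 patients if oncology rates carry over. The documents give no discontinuation rate. If 0 to 3 of 10 is assumed, the 7.1 result runs from 0% (0 to 30.8%; the upper limit is 1 − 0.025^(1/10)) to 30% (6.7% to 65.2%).

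**5. Which laboratory changes can go uncounted.** A new cycle requires ANC ≥ 1,000/mm3, platelets ≥ 75,000/mm3 and non-hematologic toxicity at Grade 1 or below, or at baseline (6.3.1). A failure delays treatment, and a delay makes the value an adverse event under 8.1.1. What remains are changes that trigger no hold, delay, dose change or intervention.
- *CBC.* Table 2-1 shows 12 post-baseline CBCs per completer: 11 at cycle starts (Days 29, 57, 85, 113, 141, 169, 197, 225, 253, 281, 309) and Day 373. At all 12, a platelet count that has fallen but is still at or above 75,000/mm3 triggers no hematologic dose rule. Thrombocytopenia, anemia and leucopenia are all named in 3.1.
- *LFTs.* Table 2-1 as extracted shows 15 post-baseline panels: the same 11 cycle starts plus Days 15, 43, 64 and 373. A Grade 1 rise triggers no dose action at any of them. A rise above Grade 1 escapes a dose rule only at Day 373 if Table 4-2 also applies mid-cycle, or at no more than those four panels if it does not. Three of the four may be local-laboratory draws sent straight to the study team (4.1), outside the 9.1 sentence, and Day 64 may be a typing or extraction slip. Hepatic events are not in the 3.1 list.

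**6. The reason given in 9.1.** Expecting abnormal values does not dispose of the 8.1.1 criterion, which concerns change from baseline. The entry limits in 5.1 (platelets ≥ 75,000/mm3, ALT and AST ≤ 3 × ULN, bilirubin ≤ 1.5 × ULN) also bound how abnormal a baseline can be.

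**The case against.** On the endpoint, one can say that the summary endpoints row, 3.1, 7.1.8 and the DMC review all agree, so 7.1 is a single outlier clause. The listed classes will be analysed, the reason for each withdrawal is recorded (6.12), and stopping rests on judgement by the DMC or investigator rather than on this test. Choosing discontinuation as the headline measure is then a preference. Much of this stands: both results would be available in a 10-patient pilot. But the list has no summary measure, 7.1 is the only place that states one, and its test still lacks a null.

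A reader might count four different endpoints. There are three contents, and two of the four places state objectives rather than endpoints. A reader might also set a low case of 4 of 10 from the 38% nausea rate in the combination studies. That cannot illustrate an any-listed-event reading when gastrointestinal events alone reach 80%.

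On laboratory changes, a reader might infer that 8.1.1 and 9.1 cancel each other, or that liver toxicity would be hidden. The documents do not support this. The action routes in 8.1.1 remain, Table 4-3 names hepatic toxicity at Grades 3 and 4, and drug is dispensed only after the monthly laboratory results are reviewed. Section 8.1.1 refers to the investigator and 9.1 to the PI, so a sub-investigator might make the judgement, though no text assigns it. Values still appear in listings and tabulations (7.1.4), and a laboratory summary could sit in the SAP that 7.1.4 mentions or in the monitoring plan still to be developed (7.1.8). Many Grade 1 changes would stay uncounted even if the PI did judge them.

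**Conclusion.** The point holds in two limited parts and should be corrected.

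First, the primary safety endpoint tested in 7.1 is not the one defined in 3.1 and carried into 7.1.8, and its test cannot be run because no null rate is stated. The summary objectives row also ranks toxicity as secondary, against Aim 1. Read as any listed event, 3.1 implies about 8 of 10 patients, assuming oncology gastrointestinal rates apply. The size of the contrast with 7.1 cannot be fixed, because the discontinuation rate is unknown.

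Second, 9.1 removes one stated route by which laboratory changes become adverse events. The loss is confined to changes that prompt no action: chiefly cytopenias above the dosing thresholds, and secondarily Grade 1 or end-of-study LFT rises. This rests on reading the 9.1 sentence as covering study CBC and LFT results taken from the medical record, and on no sub-investigator filling the gap. The number of changes affected is unknown.

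**What to change.** 1. In the summary, 2.1, 3.1 and 7.1, state that primary safety is the number of the 10 enrolled patients who discontinue because of any adverse event, reported with an exact 95% CI and no test. Tabulate the 3.1 event classes descriptively beside it. Correct the secondary label in the summary objectives row.
2. In 9.1, exempt post-baseline CBC and LFT changes from baseline from the sentence on clinical-significance determinations, so that 8.1.1 can operate.
3. Optionally, tabulate each patient's baseline and worst post-baseline CBC and LFT values from samples already drawn.

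The cost is wording in five places, a little more PI review of results already checked before dispensing, and at most one extra table. No visits or tests are added. The toxicity profile may look less favourable, and the intervals stay wide at n = 10.

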1. BACKGROUND AND STUDY RATIONALE

1.1 Scientific Background

1.1.1 Disease Under Treatment

The disease under treatment is sensitization in kidney transplant candidates. One of the major challenges in the current era of organ transplantation is to find suitable organs for highly sensitized patients defined as a cPRA > 80%. The cPRA may be calculated at <https://optn.transplant.hrsa.gov/resources/allocation-calculators/cpra-calculator/>. These patients have developed antibodies against major histocompatibility (HLA) antigens due to previous transplantation, blood transfusion, or pregnancy. Despite some success, current desensitization protocols are limited because of their complexity and lack of effective agents against plasma cells, which actually produce anti-HLA antibodies. As a result, many patients die on dialysis prior to receiving a transplant (5, 6).

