Sensitization in kidney transplant candidates. Alloantibodies (anti-HLA antibodies) arise through previous transplants, blood transfusions, and pregnancy. Currently, 39% of patients on the active kidney transplant waitlist are sensitized, evidenced by a Panel Reactive Antibody (PRA) $\geq 1\%$ (33). Of these, nearly 15,000 are highly sensitized, which means that they have a PRA $\geq 80\%$ (33). Transplant rates vary by PRA, ranging from 143.0 per 100 active waitlist years for candidates with a PRA of less than 1% to only 6.9 for those with a PRA of 98% or higher (33). Median waiting time for kidney transplantation in highly sensitized patients approaches 12 years, which is more than 3 times than for non-sensitized patients (33). As a result, a significant number of highly sensitized patients die before receiving a transplant, outlining the critical importance of desensitization strategies.

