3.2 Secondary Endpoints (efficacy endpoint)

Secondary efficacy endpoint: Successful transplantation in 12 months

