4.2 Number of Patients

A total of 10 patients will be enrolled in this pilot clinical trial. We currently have more than 40 patients that qualify for the study based on the inclusion criteria described below. A patient will be considered enrolled after the first day of ixazomib treatment.

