4.3 Duration of Study

Participants will be followed for the entire length of treatment, plus one month. All subjects, including those that receive a kidney transplant and those that do not, will continue to be monitored for one month following the last dose of study drug to monitor for and address potential adverse events from treatment (Final visit on day 373 + 6, - 3). Thereafter, dialysis nephrologists will routinely follow the patients. For those transplanted, data on acute rejection, graft and patient survival will be collected for 6 months after surgery.

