7.1.6 Efficacy Analysis

Primary outcome will be a decline in cPRA > 20%. Secondary outcome will be kidney transplantation within 12 months of therapy. These outcomes will be assessed using paired t-Test, Kaplan-Meier methods and log rank tests, where appropriate. In addition, we will analyze the change in HLA antibody strength by comparing the MFI values pre and post therapy.

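### Time to transplantation is assigned to Kaplan-Meier with no rule for death or waitlist removal; default censoring would overstate the transplant probability if such an event precedes a transplant

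*Combined protocol and SAP*

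**What the plan says.** Section 7.1 treats the secondary endpoint as a time-to-event variable: "endpoint (time to transplantation) will be assessed using Kaplan-Meier analyses and log rank tests". Other sections define it as a yes/no outcome at 12 months. Section 3.2 reads "Secondary efficacy endpoint: Successful transplantation in 12 months", the Protocol Summary agrees, and section 7.1.6 reads "Secondary outcome will be kidney transplantation within 12 months of therapy". Section 7.1.6 then covers the primary and secondary outcomes together: "These outcomes will be assessed using paired t-Test, Kaplan-Meier methods and log rank tests, where appropriate".

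No section gives a censoring rule for the time-to-transplant analysis or names a competing-risk method. Removal from the waitlist is not mentioned anywhere. Section 7.1.4 offers last observation carried forward for missing values but does not address death or delisting. Section 6.12 says withdrawn patients are not replaced, without saying how they enter this analysis.

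The background does raise death before transplant: "many patients die on dialysis prior to receiving a transplant" (section 1.1.1) and "a significant number of highly sensitized patients die before receiving a transplant" (section 1.9). Neither statement comes with a rate. The trial has one arm: "A total of 10 patients will be enrolled in this pilot clinical trial". On follow-up, section 4.3 says "Participants will be followed for the entire length of treatment, plus one month".

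**The concern.** In a single-event Kaplan-Meier analysis, anyone who leaves the risk set without the event is censored. The estimate then assumes that those censored would have been transplanted later at the same rate as those still waiting. A patient who has died, or been permanently removed from the list, cannot be transplanted later, so each later transplant is divided by too few patients.

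The error would favour the treatment. Section 7.1 hypothesises a higher transplantation rate than earlier desensitization experience, and no concurrent arm exists in which a similar error could offset it. With 10 patients, one early event changes the printed figure visibly. If the estimator is left open, it could also be chosen after the results are seen.

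**Working it through.** **The plan's own figure.** The documents give no figure for the Kaplan-Meier analysis. The nearest is the interval for 3/10 in section 7.1.1, stated there for the primary endpoint as 6.7% to 65.2%. The exact (Clopper-Pearson) limits are the 2.5% quantile of Beta(3, 8) = 6.67% and the 97.5% quantile of Beta(4, 7) = 65.25%. The figure reproduces, and the interval is 58.6 points wide.

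**Realised examples, 10 patients and 3 transplants.** 1-KM is one minus the product of (1 - 1/number at risk) over the transplants, with deaths censored.

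- No death: 1 - (9/10)(8/9)(7/8) = 30.0%.
- One death before all transplants: 1 - (8/9)(7/8)(6/7) = 1 - 6/9 = 33.3%.
- One death between the first and second transplants: 1 - (9/10)(7/8)(6/7) = 32.5%.
- One death between the second and third: 1 - (9/10)(8/9)(6/7) = 31.4%.
- One death after the last transplant: 30.0%.
- Two deaths before all transplants: 1 - (7/8)(6/7)(5/6) = 1 - 5/8 = 37.5%.

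The Aalen-Johansen estimate is 30.0% in every case. With one early death, for example, it is (9/10)(1/9) + (8/10)(1/8) + (7/10)(1/7) = 3/10. This equals the simple proportion because every patient's status is known.

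**Expected size at 12 months, constant hazards.** Let p be the transplant probability that 1-KM estimates and d the assumed annual probability of death or delisting. The hazards are lT = -ln(1 - p) and lD = -ln(1 - d). The cumulative incidence is lT/(lT + lD) x [1 - exp(-(lT + lD))].

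For p = 30% and d = 10%: lT = 0.357, lD = 0.105, and the cumulative incidence is (0.357/0.462) x (1 - 0.7 x 0.9) = 28.6%. The overstatement is 1.4 points.

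| 1-KM | d = 5% | d = 10% | d = 20% |
|---|---|---|---|
| 30% | 29.3% (+0.7) | 28.6% (+1.4) | 27.1% (+2.9) |
| 50% | 48.9% (+1.1) | 47.7% (+2.3) | 45.4% (+4.6) |

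Cells show the cumulative incidence, with the overstatement in points. Both p and d are assumptions.

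**A low anchor from the documents.** Section 1.9 gives 6.9 transplants per 100 active waitlist years for PRA of 98% or higher. With lT = 0.069, 1-KM is 6.7%. Competing hazards of 5 to 20 per 100 patient-years (also assumed) give 6.5% to 6.0%, an overstatement of about 0.2 to 0.6 points. That rate is untreated and covers a subgroup, so it marks the low end and is not a forecast.

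**The case against.** The strongest reply is that the endpoint is mostly defined so that the problem does not arise. The Protocol Summary and sections 3.2 and 7.1.6 make it transplantation within 12 months. Reported as x/10, a patient who dies simply counts as not transplanted. This stands, and it supplies the first part of the fix. It does not settle the matter, because section 7.1 names time to transplantation with Kaplan-Meier and nothing says which version will be reported.

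A second reply is that no decision rests on this endpoint. It has no threshold and no part in the sample size, and the trial is an exploratory pilot. This also stands and limits the weight of the point.

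Four stronger readings are tempting, but the documents do not support them:

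- A reader might infer that the plan censors deaths and delistings. It does not say so. Censoring is the usual default and is inferred here from silence.
- A reader might infer that death will be common during the trial. The section 1.9 statement follows a median wait approaching 12 years, and section 1.1.1 is general background. The trial covers 12 months in actively listed patients screened by section 5.2 for uncontrolled cardiovascular disease, recent serious infection and other serious illness.
- A reader might infer that the estimate must be too high. The error is zero if no competing event precedes a transplant. Study withdrawals are a separate matter: those patients may stay listed, and censoring them could push the estimate either way.
- A reader might take 30.0% in the examples as the true rate. It is an observed proportion with a wide interval.

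**Conclusion.** The point holds as a gap in the analysis rule. Kaplan-Meier is named, death and waitlist removal are not addressed, and under default censoring 1-KM exceeds the cumulative incidence whenever one of these events comes before a later transplant. Otherwise there is no error from this source.

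The expected effect is small: roughly 0.7 to 2.9 points at a 30% transplant probability and 1.1 to 4.6 at 50%. This rests on constant hazards and an assumed 5% to 20% a year for death or delisting. A realised shift can be larger, at 3.3 points for one early death and 7.5 for two, but remains well inside the 58.6-point exact interval at 3/10. It is a cheap improvement to a secondary analysis and does not threaten the trial's conclusions.

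**What to change.** In sections 7.1 and 7.1.6:

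- Report the secondary endpoint as x/10 transplanted within 12 months, with all enrolled patients in the denominator and an exact 95% CI. This matches the Protocol Summary and sections 3.2 and 7.1.6.
- For any time-to-event display, replace 1-KM with the Aalen-Johansen cumulative incidence, taking death and permanent waitlist removal as competing events.
- State how patients withdrawn under section 6.12 are handled: counted as not transplanted, or followed for transplant status to 12 months. Making death and delisting competing events does not settle this.
- List the counts transplanted, dead or delisted, and still waiting at 12 months.

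The cost is a line or so of analysis text and one data field. Deaths up to 30 days after the last ixazomib dose are already reportable as serious adverse events (sections 8.1.2 and 8.2). The schedule of events has no delisting date, so that field must be added. If withdrawn patients are to be followed to 12 months, a status check for those few patients is also needed. Design, sample size and patient care do not change.
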